2.1 Name and description of the study drugs

The test original drug Seroguard, solution manufactured by JSC Pharmasyntez, is a drug for administration into serous cavities, containing conjugate of hydrochloride 4-[4-(4-fluorophenyl)-2-[4-methylsulfinyl)phenyl]-1H-imidazol-5-pyridine with poly-1-vinylimidazole as an active ingredient. The following is information as per the draft instruction for medical use.

Structural formula

[figure not shown]

Figure 1 – Structural formula of the active ingredient of the drug Seroguard, solution

Pharmacotherapeutic group: Selective immunosuppressants

ATC code: L04AA

Pharmacodynamics

The drug doesn't exert systemic influence on organs and systems of the body. It exerts local action. It is known that in case of injured serous membrane, in particular, in case of peritoneal trauma, a hyperexpression of a set of genes is observed. They are responsible for synthesis of biologically active substances (interleukins, integrines, growth factors, signaling cascades), which launch inflammatory process and process of reparation. Hyperexpression of genes responsible for synthesis of collagen is observed from Day 3 to Day 14, maximum on Day 3. A set of gene co-expressions changed during reparative process in response to abdominal alteration is known.

Administration of Seroguard significantly modifies response of cells to alteration causing significant decrease in anti-inflammatory cytokine gene expression by Week 2 of the process, a sharp decrease of Csf3 colony-stimulating factor activation, interruption of second wave of

activation of growth factor expression, suppression of a set of genes (Egf, Pdgfa, Tgfa). Activity of Wisp1 gene happens which codes main chain of WISP signaling pathway, maintaining proliferative activity of fibroblasts and activation of Col5a3 collagen gene is significantly decreased.

Experimental studies demonstrated that during administration of Seroguard, solution, cell response is significantly changed in the site of abdomen injury from the point of view of gene activity coding proteins of focal adhesion. Main fixed shifts are an earlier activation of these gene transcription (starting from Day 1 of the process in comparison to Day 3 in control), after which an activity is sharply decreased and is left less than in control group up to the end of follow-up. Decreased expression of membrane proteins of adhesion and related proteins of cytoskeleton, probably, interferes with interaction of cells with each other and with interstitial matrix in time corresponding to conversion of fibrin adhesions into fibrous adhesions.

p38 (β , γ , δ subunits), p44 and JNK3 kinases similar by 3-dimensional structural organization act as main biological targets in the mechanism of Seroguard action, which allows to consider MAP kinase inhibition to be main in the mechanism of action of the drug.

Pharmacokinetics

After intravenous administration to rats at the dose of 6.15 mg/kg, peak of concentration is observed at about 15 minutes after administration and is 38.89 ± 2.50 $\mu\text{g/mL}$.

Half-life is 4.25 ± 0.07 h.

Mean retention time is about 5.9 hours.

Volume of distribution is about 1300 mL/kg.

After intraperitoneal administration to rats at the dose of 6.15 mg/kg, the drug in blood plasma is not observed by HPLC method, which evidences absence of its significant absorption after by the given route of administration.

Indications

Prevention of adhesions

Contraindications

Allergy to the drug components.

Intra-abdominal administration — purulent process in the abdominal cavity and the pelvis.

Gynecological surgery — purulent process in the abdominal cavity and the pelvis.

Intrapericardial administration — presence of infectious pericarditis.

Intra-articular administration — presence of infected wounds, abrasions in the joint; joint infection; venous or lymphatic stasis from the side of injured joint.

Not tested in pregnant patients, patients under 18, patients with hepatic or renal failure.

Studies in animals did not show any toxic activity or negative effect on reproductive function, fertility and teratogenic effect by Seroguard.

Posology and method of administration

Administered into serous cavity by method of single irrigation (by syringe, without injuring abdominal mesothelium) in aseptic conditions before completion of surgery. Re-administration is not recommended.

Before administration, aspirate all remaining fluids (blood, exudate, solutions administered intraoperatively).

Before use, heat the solution until body temperature.

Doses for adults:

For abdominal cavity surgery, the drug is administered at the dose of 2.4 mL/kg body weight into abdominal cavity.

For gynecological surgery, the drug is administered into abdominopelvic cavity at the dose of 1.5 to 2.4 mL/kg providing post-surgical position preventing discharge of the drug from the pelvic cavity.

For surgeries related to pericardium dissection, the drug is administered intrapericardially at the dose of 0.05 mL x left ventricular stroke output.

For administration into joint cavity during arthroscopy - up to 2 mL depending on the volume of joint.

The drug is intended only for administration into serous cavity, intravenous administration is unacceptable. Do not mix with other drugs. Do not use as a vehicle of other drugs as antibiotics, chemotherapeutic agents, etc.

Side effect

In the Phase I clinical study, general incidence of side effects on administration of the drug Seroguard was similar to those during administration of the placebo. During the study, the following side effects possibly related to administration of the drug were found: hyperthermia (1.8 %), pain in infraclavicular region (0.9 %), increased WBC count in blood (0.9 %).

Overdose

No information on overdose of the drug Seroguard is available.

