4.2.3.6 Instrumental studies

Electrocardiography

Acceptable terms of ECG performance are specified in section 4.2.4.

Standard 12-lead ECG (with measurement of heart rate [HR], PR, QRS, QT intervals and calculation of QTc) will be performed in prone position after 5 minutes of rest. Recording rhythm in the respective leads should contain evaluable data of at least three cardiac cycles. All the changes in ECG should be subjected to evaluation by a primary care physician.

If any changes in ECG, Medical Investigator should evaluate their clinical significance. If clinically significant deviations at screening, Medical Investigator should evaluate possibility of inclusion of patient into the present study, at Visit 2 and 3 or in case of unscheduled visit or withdrawal visit – to evaluate conformity to AR criteria (see section 8.2).

Ultrasound investigation of abdominal cavity and retroperitoneum

It is performed twice at Visits 0 and 2 as well as at withdrawal visit of the study as per the unique method presented in the separate guideline.

Performance of pelvic USI

Pelvic USI is performed at Visits 0 and 3 as well as at withdrawal visit of the study as per the unique method presented in the separate guideline, using transvaginal probe. Video recording of the performed investigation is required! Disc with the study results is attached to the primary documentation.

Performance of MRI of abdominal cavity and pelvis

The study is performed under fasting conditions (a female patient should starve before the investigation for at least 4 hours). 0.5 – 1.0 hours before the investigation, a female patient should

void the bladder and colon. Before the investigation, features of abdominal cavity and pelvic MRI performance will be explained to a female patient in detail.

MRI of the abdominal cavity and the pelvis is performed at Visits 0 and 3, as well as at withdrawal visit as per the protocol of MRI investigation which will be provided in a separate guideline along with evaluation of adhesion severity according to the following method defined by the Sponsor:

Prevalence in abdominal cavity:

1. absence of adhesions;
2. one floor (up to 3 segments of one level);
3. two floors;
4. total adhesive process.

Prevalence in pelvic cavity:

1. Absence;
2. One region (right lateral space, left lateral space, pouch of Douglas or vesicouterine pouch);
3. Two regions;
4. Subtotal adhesive process in the pelvis (3 regions);
5. Total adhesive process in the pelvis.

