4.2.4.2 Therapy period

Visit 1 (Day 0)

Before the surgery:

- Physical examination (see section 4.2.3.2).
- Evaluation of vital signs (see section 4.2.3.3).
- Actualization of the information on concomitant therapy.
- Actualization of the information on concomitant diseases.

- Re-evaluation of inclusion/non-inclusion criteria (see section 5).
- Randomization (see section 4.3.1).
- ***Surgical intervention using the test drug or the placebo***

After the surgery:

- Physical examination (see section 4.2.3.2).
- Evaluation of vital signs (see section 4.2.3.3).
- Evaluation of local status (condition of postsurgical wounds). (see section 4.2.3.4)
- Evaluation of AR (see section 8).

Visit 2 Interim safety assessment (Day 6±1)

- Physical examination (see section 4.2.3.2).
- Evaluation of vital signs (see section 4.2.3.3).
- Evaluation of local status (condition of postsurgical wounds). (see section 4.2.3.4) .
- Evaluation of withdrawal criteria (see section 5.3)
- Laboratory investigations: complete blood count, blood chemistry, urinalysis (see section 4.2.3.5).
- USI of the abdominal cavity (see section 4.2.3.6).
- ECG (see section 4.2.3.6).
- Actualization of the information on concomitant therapy.
- Actualization of the information on concomitant diseases.
- Evaluation of AR (see section 8).

Visit 3 (30±4) Evaluation of safety and efficacy

- Physical examination (see section 4.2.3.2).
- Evaluation of vital signs (see section 4.2.3.3).
- Evaluation of local status (condition of postsurgical wounds).
- Laboratory investigations: complete blood count, blood chemistry, coagulogram, urinalysis, pregnancy test (see section 4.2.3.5).
- USI of pelvic organs (transvaginal) (see section 4.2.3.6).
- MRI of the abdominal cavity and the pelvis (see section 4.2.3.6).
- ECG (see section 4.2.3.6)
- Actualization of the information on concomitant therapy.

- Actualization of the information on concomitant diseases.
- Evaluation of AR (see section 8).

4.2.4.3 *Unscheduled visit*

Unscheduled visit may be performed at the discretion of the Investigator in case of ARs for performance of the required investigations. During each unscheduled visit regardless of its reason, the Investigator performs the following procedures and completes respective pages of CRF (Additional/Unscheduled visit):

- Physical examination (see section 4.2.3.2).
- Evaluation of vital signs (see section 4.2.3.3).
- Evaluation of local status (condition of postsurgical wounds).

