5.2 Non-inclusion criteria

1. Female patients having contraindications to operative treatment (including acute or exacerbated chronic adnexal inflammatory process)
2. Body mass index 30.0 kg/m^2 and more
3. Known hypersensitivity to components of the test drug (Seroguard)
4. Pregnancy, lactation or planning for pregnancy during the clinical study
5. Refusal to use effective contraception methods throughout the study
6. Positive HIV, RW, HBV or HCV test results.
7. Alcohol abuse, drug addiction, and toxicomania (except for smoking)
8. Category III and higher by physical status classification of the American Society of Anesthesiologists (ASA).
9. Purulent process in the abdominal cavity
10. Disseminated endometriosis
11. Elevated WBC count in complete blood count exceeding $10 \times 10^9/\text{L}$

12. Necessity of using any other drugs during the surgery (except for 0.02% chlorhexidine aqueous solution throughout the surgery, as well as the test drug or the placebo (0.9% sodium chloride) in the end of surgery) administered intraperitoneally
13. Concomitant diseases that may require conversion of the surgical intervention by other indications
14. Type I or II diabetes mellitus
15. Deep vein thrombosis and/or PATE at screening or in the history
16. Renal impairment (reduced glomerular filtration rate below 60 mL/min/1.73 m² evaluated by the CKD-EPI equation)
17. Liver disorders determined as more than 2-fold elevation of the upper limit of normal of one of the following enzymes: ALT, AST, GGTP, AP, or more than 2-fold elevation of total bilirubin level
18. Myocardial infarction within 6 months before screening
19. Any concomitant diseases accompanied by heart failure.
20. Clinically significant changes in ECG (in Investigator's opinion).
21. Any concomitant diseases accompanied by respiratory failure
22. Any oncology disease within 3 years before enrollment into the study.
23. Systemic inflammatory diseases.
24. Diseases associated with chronic hemorrhages
25. Blood diseases (anemias of any origin, hemoglobinopathies, inherited and acquired coagulopathies, hemostasis disorders, thrombocytopenias, and thrombocytopathias, any hemoblastoses)
26. Any other disease, that, in the Investigator's opinion, may distort the study results or present an additional threat to well-being of a female patient after administration of the study drug

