5.3 Withdrawal criteria

1. Withdrawal of informed consent by female patient
2. Female patient's non-compliance with the rules of participation in the study.
3. Pregnancy occurrence.
4. Necessity of conversion during surgical intervention
5. Necessity of surgery during the period between adhesiolysis surgery and Visit 3
6. Other reasons occurring during the study and interfering with the study performance in accordance with the protocol.
7. Necessity of drain tube installation revealed during the surgery

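### The drug's contraindication names the pelvis, non-inclusion criterion 9 does not, and no withdrawal criterion names a purulent finding made at laparoscopy

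*Protocol*

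**What the plan says.** The drug information appears twice in the Protocol, in 2.1 and 4.4.1. Both places carry a contraindication specific to this kind of operation: for gynaecological surgery, a "purulent process in the abdominal cavity and the pelvis".

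Non-inclusion criterion 9, in the Synopsis and in 5.2, is shorter: "Purulent process in the abdominal cavity".

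Three other non-inclusion criteria bear on pelvic infection:
- Criterion 1 excludes women with contraindications to the operation and gives acute or flaring chronic adnexal inflammation as an example.
- Criterion 11 reads "Elevated WBC count in complete blood count exceeding" 10 × 10⁹/L.
- Criterion 26 leaves to the investigator any other disease that would add to the patient's risk after dosing.

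At Visit 1 (4.2.4.2) the second eligibility check stands among the steps before surgery, ahead of randomization. Section 4.2.1 places instillation at the final stage of the operation.

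Section 5.3 has seven withdrawal criteria. Two concern events during the operation: conversion (criterion 4) and "Necessity of drain tube installation revealed during the surgery" (criterion 7). Criterion 6 is a general clause.

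**The concern.** The trial treats pelvic adhesions, and the pelvis is the site missing from the eligibility wording. A site that works from the section 5 lists, using the protocol's own terms, could find criterion 9 not met in a woman to whom the contraindication applies.

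A second gap follows from timing. The surgeon sees the pelvis after the last scheduled eligibility check and before the solution goes in. The protocol provides for some findings at that stage but does not name this one.

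At stake is the protection of individual women. Section 2.1 classes the product as a selective immunosuppressant with local action, and it is placed in the cavity concerned. Consistency between sites is also at stake, because where no rule is named the decision falls to each investigator.

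**Working it through.** No arithmetic applies, and the plan states no figure on this point to reproduce. The check sets the passages side by side.

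| Place | Abdominal cavity named | Pelvis named |
|---|---|---|
| 2.1, contraindication for gynaecological surgery | yes | yes |
| 4.4.1, same contraindication | yes | yes |
| Synopsis, criterion 9 | yes | no |
| 5.2, criterion 9 | yes | no |

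**Does the abdominal cavity include the pelvis here?** Not plainly. The contraindication names both. The MRI scoring in 4.2.3.6 has one scale for the abdominal cavity and another headed "Prevalence in pelvic cavity". Table 1 lists ultrasound of the abdominal cavity and of the pelvic organs as separate procedures with different visit schedules.

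**Do other criteria close the gap before surgery?** In part.
- Criterion 1 is framed as a limit on operating, not on instilling the drug, and its example is adnexal inflammation.
- Criterion 11 rests on a blood count that Table 1 schedules at screening (Day -15 to Day -1) and does not repeat at Visit 1.
- Criterion 26 depends on the investigator's opinion.

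Together they exclude some pelvic infection, but none states the contraindication's limit.

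**What applies to a finding made during the operation?**
1. Eligibility is re-checked before surgery (4.2.4.2).
2. Table 1 marks evaluation of withdrawal criteria at Visit 2 and the unscheduled visit, with no mark at Visit 1. The visit descriptions in 4.2.4.2 and 4.2.4.3 agree.
3. The solution is given at the end of surgery (4.2.1).
4. None of the seven criteria in 5.3 names a purulent finding.
5. Criterion 6 is wide enough to be read as reaching it.
6. Section 5.3.1 gives two possible grounds after randomization: a danger to the patient's safety, and a disease from the non-inclusion list. Both are discretionary, because the investigator may exclude. The second refers back to the list that omits the pelvis, and it carries a qualifier about drugs the protocol does not permit.

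So such a finding is not named, and it is reachable only through general or discretionary wording.

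**The case against.** The strongest reply is that a woman with a pelvic purulent process is unlikely to reach dosing. Screening includes gynaecological examination, transvaginal ultrasound, pelvic MRI and smear microscopy, besides criteria 1, 11 and 26. At surgery, a drain or conversion leads to withdrawal under 5.3, and so does the need for a forbidden intraperitoneal drug under 6.2.2. Sites also have the contraindication itself, printed twice, and 4.4.4 refers dosing to the draft package insert. All of this stands, and it makes the gap small. It does not make the two texts agree.

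The terminology can also be argued the other way. The same instillation is described as going into the abdominal cavity (4.4.4), the pelvic cavity (6.3.1) and the abdominopelvic cavity (2.1), so a reader might take criterion 9 to include the pelvis. That shows the term is used inconsistently, which is itself a reason to state the limit once.

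A reader might infer more than the documents support:
- **That nothing in the withdrawal rules covers such a finding.** Criterion 6 and 5.3.1 can be read to cover it. The supportable statement is that none of the criteria names it.
- **That membership of the analysis set would vary by site.** Section 9.7.1 fixes the rule: randomized and given the study drug. What can vary is the decision to instil.
- **That any resulting infection would count as a drug reaction.** Section 8.2 grades causality and has categories for other explanations, and the placebo groups enter under the same eligibility rules.

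**Conclusion.** The inconsistency is real: the contraindication in 2.1 and 4.4.1 names the pelvis, and criterion 9 in the Synopsis and 5.2 does not. The handling of a purulent finding at laparoscopy is incomplete, because it rests on general or discretionary grounds while two other intraoperative events are named. This is a correction of wording with a patient-safety purpose.

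Its size cannot be given as a number, because the document has no figure for how often such findings occur. It is tempting to express it as one event among the 26 women randomized per group (1/26 = 3.8 percentage points). That ratio holds for any single event in any group and does not measure this defect. The 5% significance level, the 80% power and the planned numbers are unaffected.

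The conclusion assumes that the contraindication is meant to apply to each site it names and that the listing in 2.1 and 4.4.1 is current. Section 2.2.1 reports a therapeutic effect in modelled purulent peritonitis. That does not remove the contraindication, but it is a further reason for the protocol to state one position.

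**What to change.** Reconcile criterion 9 in the Synopsis and 5.2 with the contraindication in 2.1 and 4.4.1, so that the same anatomical limit stands in all four places. Then reconcile the withdrawal lists (Synopsis and 5.3) and the Visit 1 checks (4.2.4.2 and Table 1) with that limit, so that the protocol says how a finding made after the last eligibility check and before instillation is handled. The sponsor decides what the limit and the handling are; this review proposes neither.

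The cost is amendment wording in the affected lists and in the Visit 1 schedule. The sample size calculation and the primary analysis stay as they are.

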2.2 Results of pre-clinical and clinical studies significant for the given study

2.2.1 Pre-clinical studies

Experimental studies of safety of Seroguard, solution were performed. They were aimed at evaluating acute and chronic toxicity, irritant properties, allergenicity, immunotoxicity, reproductive toxicity, mutagenicity and risk of carcinogenic action.

The test drug was proved to be low toxic, to have a high therapeutic index and safe after long-term (180 days) daily intraperitoneal administration to endotherm animals (rodents and dogs). Solution

of the drug does not exert irritant action at the site of administration and is apyrogenic. It was shown that the drug does not have specific types of toxicity.

The performed studies showed that administration of Seroguard during modelling aseptic and purulent peritonitis had a marked therapeutic action and contributed to prevention of adhesions.

After intravenous administration to rats at the dose of 6.15 mg/kg, peak concentration is observed about at 15 minutes after administration and is $38.89 \pm 2.50 \mu\text{g/mL}$. Half-life is 4.25 ± 0.07 h. Average retention time is about 5.9 hours. Distribution volume is about 1300 mL/kg. After intraperitoneal administration to rats at the dose of 6.15 mg/kg, the drug is not observed in blood plasma which evidences absence of its significant absorption during the given route of administration.

According to hazard classification of drug products for clinical use, Seroguard, solution is referred to class III of low-toxic (low-hazard) drugs.

2.2.2 Clinical studies

Seroguard, solution is a new original drug that has passed pre-clinical studies, Phase I clinical study was also performed (19). Multi-center double-blind placebo-controlled study included patients of both genders at the age from 18 to 75 years having indications for planned laparoscopic cholecystectomy. Treatment group (Seroguard) included 24 patients, and placebo group (0.9% sodium chloride) - 23 patients. Seroguard, solution 0.41 g/L, JSC Pharmasyntez, Russia or its respective placebo were administered into abdominal cavity at the end of laparoscopic cholecystectomy at the dose of 2.4 mL/kg. Incidence, nature and severity of adverse reactions (including clinically significant abnormalities of physical examination, vital signs, instrumental investigations, clinical laboratory parameters) were evaluated. 206 adverse reactions (AR) were recorded in the study: 110 (53,4%) – in the group of treatment with Seroguard and 96 (46.6%) – in the placebo group. 14 cases of adverse reactions (6.8%) were moderate and one was severe, remaining adverse reactions were mild. 194 (94.2%) ARs were doubtfully related to administration of the drug, 8 (3,9%) – conditionally related, and 4 ARs (1,9%) in the treatment group were evaluated as possibly related to the drug administration. 196 of 206 ARs (95.2%) completed by recovery of patient, in the remaining 10 cases (4.9%), a significant amelioration was observed. 4 serious ARs were also recorded in three patients of both groups in the study.

No statistically significant changes, except for level of eosinophils and lymphocytes in the placebo group, were recorded in most of complete blood count and blood chemistry parameters. A statistically significant elevation ($p = 0.0297$) was noted in the level of eosinophils in the placebo group by Visit 11 (Day 28), however, it was not clinically significant. Similarly, elevation in lymphocytes ($p = 0,0148$) was observed by Visit 11 (Day 28), which was not clinically significant.

The performed analysis of coagulogram data did not reveal statistically significant differences in any parameter between the Visits ($p > 0.05$). Analysis did not also show any statistically significant variations in vital signs ($p > 0.05$).

Thus, a good tolerability (comparable to that of placebo) of the drug Seroguard, solution 0.41 g/L, JSC Pharmasyntez, Russia was proved after administration into abdominal cavity at the end of laparoscopic cholecystectomy at the dose of 2.4 mL/kg in the Phase I study.

More detailed information on results of pre-clinical studies is provided in the Investigator's Brochure.

